# **9.6.1. Data collection tools (DCTs)**

As used in this protocol, the term DCT should be understood to refer to either a paper form or an electronic data record or both, depending on the data collection method used in this study.

A DCT is required and should be completed for each included patient for whom outcomes are being adjudicated via medical record review- electronic health record note snippet review. The completed original DCTs are maintained by Optum and should not be made available in any form to third parties, except for appropriate regulatory authorities, without written permission from Pfizer. Optum shall ensure that the DCTs are securely stored at the study site in encrypted electronic form and will be password protected to prevent access by unauthorized third parties.

Optum has ultimate responsibility for the collection and reporting of all clinical, safety, and laboratory data entered on the DCTs and any other data collection forms (source documents) and ensuring that they are accurate, authentic/original, attributable, complete, consistent, legible, timely (contemporaneous), enduring, and available when required. The DCTs must be signed by the investigator or by an authorized staff member to attest that the data contained on the DCTs are true. Any corrections to entries made in the DCTs or source documents must be dated, initialed, and explained (if necessary) and should not obscure the original entry.

The source documents are the hospital or the physician's chart note snippets from the electronic health record. In these cases, data collected on the DCTs must match those charts notes.

#### 9.6.2. Record Retention

To enable evaluations and/or inspections/audits from regulatory authorities or Pfizer, Optum agrees to keep all study-related records, including sufficient information to link records, (e.g., DCTs and hospital records encrypted note snippets), electronic copies of all DCTs, safety reporting forms, source documents, and adequate documentation of relevant correspondence (e.g., letters, meeting minutes, and telephone call reports). The records should be retained by Optum according to local

regulations or as specified in the Optum contract, whichever is longer. Optum must ensure that the records continue to be stored securely for so long as they are retained.

If Optum becomes unable for any reason to continue to retain study records for the required period, Pfizer should be prospectively notified, and study records should be retained under an arrangement acceptable to Pfizer that protects the confidentiality of the records (e.g., secure off-site storage). Study records must be kept for a minimum of 15 years after completion or discontinuation of the study, unless Optum and Pfizer have expressly agreed to a different period of retention via a separate written agreement.

If Pfizer would like the Study Records kept longer than the 15-year retention period, Pfizer will notify Optum prior to the end of the 15-year retention period.

## 9.7. Data analysis

# **Primary objective**

In primary analyses, descriptive statistics will be presented to characterize myocarditis patients in terms of demographic and clinical characteristics (including clinical characteristics of the myocarditis episode, as well as clinical history of the patient) as of the index date (date of myocarditis diagnosis code for myocarditis cases, or matched month/year among the control group). Specific demographics and clinical characteristics of interest are described in Section 9.3. Descriptive statistics will include counts and percentages for categorical data. For continuous variables, we will provide statistics such as mean, median, standard deviation, and range.

Additionally, appropriate statistical models such as conditional logistic regression or generalized estimating equations (GEE) incorporating non-independence of observations will be described in greater detail in the SAP. These models will estimate odds ratios (ORs) and 95% CIs of associations between demographics, clinical characteristics, and empirical model identified risk factors (based on either a stepwise selection approaches or via statistical significance in univariate models) and myocarditis. Models may incorporate laboratory based prognostic indices, severity status, clinical risk factors noted in Section 9.3 along with potential empirical model identified risk factors. These models will be run for the myocarditis cases and controls identified with ICD-10-CM codes in the EHR, and according to the inclusion and exclusion criteria as provided in Section 9.2, as well as for the cases that are validated by clinician reviews as myocarditis using the available Brighton Collaboration Criteria and information in medical record notes, as specified in Section 9.6. Model parameters will be detailed in the SAP.

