# Primary objective:

1. To assess and compare demographic, medical history, and comorbidities that may be risk factors for myocarditis in each of three cohorts: 1) Myocarditis after mRNA COVID-19 vaccine, 2) Myocarditis after SARS-CoV-2 infection (2020-2022), or 3) Acute/viral myocarditis prior to the COVID-19 era (pre-2020).

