### 9.5. Study size

This is a NI study with no *a priori* hypotheses specified; therefore, sample size calculations are not applicable. Based on initial feasibility assessment of the Optum EHR database, there were approximately 240 myocarditis cases within 21 days of mRNA vaccination, 1,730 myocarditis cases after SARS-CoV-2 infection, and 7,200 myocarditis cases prior to 01 November 2019. In addition, the large size of the database will allow for matching of each myocarditis case with controls for the risk factor analyses.

 CFR 164.514(b)(1).

<sup>[2] Guidance Regarding Methods for De-identification of Protected Health Information in Accordance with the Health Information Insurance Portability and Accountability Act (HIPAA) Privacy Rule (Dated as September 4, 2012, as first released on November 26, 2012).

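### Empirical risk factors are selected by p-value and then reported with ordinary 95% CIs from the same data, so those intervals lack nominal coverage and modest odds ratios are inflated in the vaccine cohort of about 240 cases

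*Protocol*

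**What the plan says.** The primary objective in section 8 is "To assess and compare demographic, medical history, and comorbidities that may be risk factors for myocarditis in each of three cohorts".

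For this objective, section 9.7 plans descriptive statistics and then regression: "These models will estimate odds ratios (ORs) and 95% CIs of associations between demographics, clinical characteristics, and empirical model identified risk factors". The last group in that sentence is chosen "based on either a stepwise selection approaches or via statistical significance in univariate models". The next sentence allows the models to include "clinical risk factors noted in Section 9.3 along with potential empirical model identified risk factors". The abstract repeats the selection rule. Neither place mentions shrinkage, a hold-out sample, multiplicity control or any adjustment of the intervals for selection. Section 9.7 names no method for comparing the cohorts.

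Section 9.5 gives feasibility counts of "approximately 240 myocarditis cases within 21 days of mRNA vaccination, 1,730 myocarditis cases after SARS-CoV-2 infection, and 7,200 myocarditis cases" before 1 November 2019, and sets aside study-size reasoning because there are no a priori "hypotheses specified; therefore, sample size calculations are not applicable".

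Section 9.7 leaves model parameters to the SAP. It also says that major changes to primary endpoint definitions or their analyses would be reflected in a protocol amendment.

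**The concern.** Both permitted routes let a factor in because its estimate was far enough from the null in these data. A 95% CI computed afterwards as if the factor had been fixed in advance is conditional on that event and ignores it. Two consequences follow:

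- Null factors that pass are reported with intervals that exclude 1.
- True factors pass more often when chance has pushed their estimate upward, so a small cohort reports them too large.

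The second effect depends on cohort size, and the cohorts differ 30-fold (7,200 / 240). The objective is to compare them, and 9.7 offers significance as its only rule for identifying empirical factors. A reader of the results could then take a factor that is listed before COVID but absent after vaccination as a real contrast when only the precision differs.

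**Working it through.** **Inputs.** The counts 240, 1,730 and 7,200 are from section 9.5. The protocol gives no power figure to reproduce. Everything else here is assumed: two-sided selection alpha 0.05 (to match the 95% CIs), 4 controls per case, control prevalence 10%, 100 candidates of which 10 are true, true OR 1.2 to 2.0. Matching is ignored throughout.

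**1. Null factors.** Expected false entries = 0.05 × number of null candidates, so 5 per 100 in each cohort whatever its size. If the model that selects the factor also gives the interval, p < 0.05 is the same event as a 95% CI that excludes 1. Coverage for a selected null factor is then 0.

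**2. Size an OR must reach to be selected.** SE(log OR) = √(1/a + 1/b + 1/c + 1/d). For Cohort 1 at OR 1.3, exposure among cases is 0.13 / (0.90 + 0.13) = 12.6%. This gives expected cells a = 30.3, b = 209.7, c = 96, d = 864 and SE = 0.222. The smallest estimate that reaches significance is exp(1.96 × 0.222) = 1.55, which is above the true value of 1.3. The same calculation gives SE 0.083 and threshold 1.18 in Cohort 2, and SE 0.041 and threshold 1.08 in Cohort 3.

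**3. Selection power and mean reported OR given selection** (power by the two-proportion formula; mean OR from 200,000 simulated 2×2 tables per setting, geometric mean):

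| True OR | Power, Cohorts 1 / 2 / 3 | Mean OR if selected, Cohorts 1 / 2 / 3 |
|---|---|---|
| 1.2 | 13% / 57% / 99% | 1.70 / 1.27 / 1.20 |
| 1.3 | 23% / 87% / 100% | 1.72 / 1.33 / 1.30 |
| 1.5 | 48% / 100% / 100% | 1.78 / 1.50 / 1.50 |
| 2.0 | 91% / 100% / 100% | 2.07 / 2.00 / 2.00 |

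With 1:1 matching in Cohort 1, a true 1.3 becomes 2.08.

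**4. False share of the list.** Share = FP / (FP + TP), with FP = 0.05 × 90 = 4.5 and TP = 10 × power.

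- OR 1.3: Cohort 1, 4.5 / (4.5 + 2.3) = 66%; Cohort 2, 4.5 / (4.5 + 8.7) = 34%; Cohort 3, 4.5 / (4.5 + 10) = 31%.
- OR 1.5: Cohort 1, 4.5 / (4.5 + 4.8) = 48%; Cohorts 2 and 3, 31%.
- Univariate screening followed by backward elimination (simulated), Cohorts 1 / 2 / 3: 73% / 34% / 40% at OR 1.3 and 50% / 32% / 35% at OR 1.5. Only 20 runs were made for Cohort 2 and 5 for Cohort 3.
- Extremes for OR 1.3 to 1.5. Few candidates, many true (50 and 20): Cohort 1, 1.5 / (1.5 + 9.6) = 13 to 14%; Cohort 3, 1.5 / 21.5 = 7%. Many candidates, few true (300 and 5): Cohort 1, 14.75 / (14.75 + 1.15) = 93%; Cohort 3, 14.75 / 19.75 = 75%. Cohort 2 runs from 7% to 77%.

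**5. Coverage.** In the same two-stage simulation, nominal 95% CIs of the selected factors covered the truth in 22 to 64% of instances. The full prespecified 100-factor model covered in 92 to 94%. The shortfall comes mainly from the selected null factors. For a true OR of 1.3 that is selected, univariate coverage is 88% in Cohort 1 and about nominal in Cohorts 2 and 3.

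**6. Comparing lists when the true OR is identical.** The probability that exactly one of Cohorts 1 and 3 lists the factor is P1(1 − P3) + P3(1 − P1). At OR 1.2 the simulated selection rates are 0.145 and 0.991, which gives 0.145 × 0.009 + 0.991 × 0.855 = 0.85. At OR 1.3, 1.5 and 2.0 it is 76%, 51% and 8%. A direct test, (log OR1 − log OR3) / √(SE1² + SE3²), finds a false difference in about 5% at every OR.

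**The case against.** The strongest defence is about scope. The selection phrase qualifies only the third group in the sentence; demographics and clinical characteristics come before it, and section 9.3 factors may enter unscreened. This stands. A reader might infer that the whole comorbidity, drug and laboratory pool is screened, that important confounders are dropped, or that each cohort ends up adjusted for a different set. The text does not establish any of these, although entry of the section 9.3 factors is optional as worded.

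Second, a reader might infer that most reported factors will be false. The figures do not support that as a general statement. It fits Cohort 1 with weak effects or many candidates. In Cohorts 2 and 3 the base case is about a third, and every share depends on inputs the protocol does not give.

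Third, a reader might infer that the between-cohort comparison will simply reflect cohort size. No section says the cohorts will be compared by significance; ORs with CIs can be compared by magnitude and precision. The effect also fades at OR 2.0. In addition, the 30-fold ratio belongs to the code-based run, because only a sample of pre-2020 cases goes to note review and the ratio among validated cases is unknown.

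Fourth, the study has no prior hypotheses, hypothesis generation is one stated aim, and model detail is left to the SAP. This justifies having an exploratory screen. It does not justify reporting the screen's output with unadjusted 95% CIs inside the primary analysis. That rule is written in the protocol, not deferred. Section 7 also intends the results to help mitigate safety events and to inform future trial eligibility.

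**Conclusion.** The point holds for the empirically selected factors. As written, 9.7 gives them intervals without nominal coverage and admits about 5 null factors per 100 null candidates per cohort, given a selection alpha of 0.05. In Cohort 1 modest effects are inflated (1.3 to about 1.7, 1.5 to about 1.8, at 1:4 and 10% prevalence); inflation is small in Cohort 2 and negligible in Cohort 3.

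With 100 candidates, 10 true and OR 1.3 to 1.5, the false share is roughly 50 to 70% in Cohort 1 and 31 to 40% in Cohorts 2 and 3. It ranges widely under other assumptions. The comparison problem is conditional: it arises if selected lists are compared, which the protocol leaves open. In that case identical ORs of 1.2 to 1.5 would look different between Cohorts 1 and 3 in about 51 to 85% of cases.

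The loss of coverage and the direction of the inflation follow from the stated rule. The sizes rest on the assumed inputs and on calculations that ignore matching.

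**What to change.** Change the sentence in section 9.7 and its copy in the abstract:

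1. The primary model uses one prespecified covariate list drawn from section 9.3, identical in all three cohorts, with every OR and 95% CI reported whatever its p-value.
2. Empirical selection becomes a separate step labelled exploratory. Its post-selection intervals are not presented as nominal 95% CIs.
3. The comparison in the primary objective is made by ratios of ORs between cohorts with 95% CIs, from cohort-by-factor terms, not by which factors were selected where.

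The choice of penalisation, false-discovery-rate control or bootstrap for step 2 can be left to the SAP, because it involves a real trade-off. In the simulation, Benjamini-Hochberg at 5% cut false selections from about 4 to 7 per cohort to about 0.2 to 1.6, but in Cohort 1 it kept only 0.3 (OR 1.3) or 1.1 (OR 1.5) of 10 true factors.

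The cost is protocol wording, modest extra programming and visibly wide Cohort 1 intervals. At OR 1.3 under the assumptions above, the SE of the log ratio of ORs for Cohort 1 against Cohort 3 is √(0.222² + 0.041²) = 0.226, so its 95% CI spans a factor of exp(1.96 × 0.226) = 1.56 in each direction. That width is an honest statement of what about 240 cases can show.

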To date, for myocarditis of any cause, only younger age, male gender, as well as engagement in competitive athletics were established as risk factors for myocarditis.  Population studies show that incidence of myocarditis tends to peak around adolescence through 40 years of age.  During pre-COVID-19 timeframes, the female-to-male ratio was between 1:1.5 and 1:1.7 in series of patients with myocarditis.  Outside of these characteristics, an understanding of risk factors that predispose individuals or contribute to the development of myocarditis after exposure to infections or drugs/vaccines is limited.

Higher myocarditis risk has been reported after SARS-CoV-2 infection, ranging from 5.4 per 100,000 persons (54 per million) for girls 5-11 years to 57.2 per 100,000 persons (572/million) for males 30 years of age or older within a 7-day risk window of infection. Heymans and Cooper

reviewed a variety of studies and concluded that SARS-CoV-2 infection caused 1000 to 4000 cases of myocarditis per 100,000 people, which was higher than most other reports. In a large meta-analysis, Ling et al. reported SARS-CoV-2 infection caused 1100 cases of myocarditis per 100,000 people. After the acute natural infection, from which most recover, long-term cardiovascular sequelae are possible. The risk and 1-year burden of cardiovascular disease in survivors of acute COVID-19 are substantial, with increased risk of cerebrovascular disorders (stroke, transient ischemic attack), dysrhythmias, ischemic and non-ischemic heart disease, pericarditis, myocarditis, heart failure, and thromboembolic disease.

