- Controls risk-set matched on e.g. month/year of cohort entry, duration of follow up (from cohort entry), integrated delivery network (IDN). Matching criteria will be detailed in the SAP.
- Timeframe for each myocarditis sub-cohort:
  - 1) Post-vaccination myocarditis: December 11, 2020 November 01, 2022
  - 2) Post-SARS-CoV-2 myocarditis: January 01, 2020 November 01, 2022
  - 3) Pre-COVID era myocarditis: January 01, 2016 November 01, 2019

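### Section 9.7 allows risk factors to be selected by univariate significance without requiring that age and sex be controlled, so age-related factors can be masked if that route is taken with age and sex unmatched

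*Protocol*

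**What the plan says.** The primary objective (Section 8) is "To assess and compare demographic, medical history, and comorbidities that may be risk factors for myocarditis" in each of three cohorts. Section 9.7 plans "appropriate statistical models such as conditional logistic regression or generalized estimating equations (GEE) incorporating non-independence of observations". These are to report odds ratios for demographics, clinical characteristics and empirically identified factors, the last chosen either by stepwise selection or "via statistical significance in univariate models". The abstract repeats this. Section 9.7 adds that models may also contain "clinical risk factors noted in Section 9.3 along with potential empirical model identified risk factors".

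Three other places bear on the point:

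- Section 7 states that, for myocarditis of any cause, "only younger age, male gender, as well as engagement in competitive athletics were established as risk factors for myocarditis". It also lists male sex and younger age among the only factors identified for post-vaccine cases.
- Section 9.2.1 admits all ages.
- Section 9.1 and the notes to Figure 1 give example matching factors: encounter month, database activity, month and year of cohort entry, length of follow-up, and delivery network. Age and sex are not among the examples. The notes add that "Matching criteria will be detailed in the SAP".

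As secondary analyses, Section 9.7 repeats everything by case definition, age group, sex and follow-up time.

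**The concern.** A univariate model for a comorbidity contains that comorbidity and nothing else. Unless age and sex are held fixed by matching, it compares cases that the protocol expects to be younger and more often male with controls drawn from all ages. Many chronic conditions become more common with age. For those, the younger case mix pulls the crude odds ratio below its true value. A real risk factor can then look null, fail the screen and never reach the adjusted model, while a condition with no effect can look protective and pass.

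This is confounding, so a larger sample does not remove it. It is also separate from the usual multiplicity objection to data-driven selection. The primary objective compares risk factors across cohorts. If the age mix of cases relative to controls differs between cohorts, the selected lists could differ for that reason alone.

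**Working it through.** The protocol gives no alpha, power, control ratio, age mix or comorbidity prevalence, so it has no figure to reproduce. From the protocol: about 240, 1,730 and 7,200 cases in Cohorts 1, 2 and 3 (Section 9.5), and 40 years as an example age cut (Section 9.7). Everything else is assumed, and only age is modelled.

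**Base scenario.** Assume 70% of cases and 35% of controls are under 40. Comorbidity prevalence in controls is 5% under 40 and 30% from 40. The true odds ratio is 2.0 in both strata, with 240 cases, 960 controls and two-sided alpha 0.05.

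*Crude odds ratio.* Prevalence in cases within a stratum is p×OR / (1 − p + p×OR).

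- Under 40: 0.10/1.05 = 0.0952. From 40: 0.60/1.30 = 0.4615.
- All cases: 0.70×0.0952 + 0.30×0.4615 = 0.2051.
- All controls: 0.35×0.05 + 0.65×0.30 = 0.2125.
- Crude odds ratio: (0.2051/0.7949) / (0.2125/0.7875) = 0.96.

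*Chance of passing the univariate screen.* The standard error of the log odds ratio is the root of the summed reciprocal cell counts: √(1/49.2 + 1/190.8 + 1/204 + 1/756) = 0.178. Then z = ln(0.956)/0.178 = −0.25. The chance of p < 0.05 is about 6%, and only about 1% in the correct direction.

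*Age-stratified test.* The stratum standard errors are √(1/16 + 1/152 + 1/16.8 + 1/319.2) = 0.363 and √(1/33.2 + 1/38.8 + 1/187.2 + 1/436.8) = 0.252. The inverse-variance combination is 1/√(1/0.363² + 1/0.252²) = 0.207. Then z = 0.693/0.207 = 3.35, and power is about 92%.

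*A factor with no effect.* Case prevalence is 0.70×0.05 + 0.30×0.30 = 0.125. The crude odds ratio is (0.125/0.875)/(0.2125/0.7875) = 0.53, with standard error √(1/30 + 1/210 + 1/204 + 1/756) = 0.21. Then z = −3.02, so it passes the screen about 86% of the time as apparently protective.

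**Other assumed inputs.** True odds ratio 2.0, 40% of controls under 40, 240 cases, 4 controls per case. Screen figures are from a two-proportion test; the Wald test used above agrees within about 2 percentage points.

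| Cases under 40 | Prevalence <40 / 40+ | Crude OR | Screen significant | Age-stratified power |
|---|---|---|---|---|
| 55% | 3% / 20% | 1.46 | 51% | 92% |
| 70% | 3% / 20% | 1.08 | 6% | 85% |
| 80% | 3% / 20% | 0.84 | 11%, almost all in the wrong direction | 77% |
| 40% (same as controls) | 3% / 20% | 1.89 | 92% | 95% |
| 70% | 10% / 12% | 1.88 | 88% | 93% |

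**Effect of size.** In the second row, the screen is significant 16% of the time with 1,730 cases and 50% with 7,200. The stratified test is near 100% at both sizes.

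The last two rows of the table show the limits. With equal age mix, or a comorbidity that hardly varies with age, masking almost vanishes. The 1.89 in the fourth row falls short of 2.0 only because odds ratios are not collapsible over age.

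**The case against.** The strongest reply is that the protocol does not commit to this analysis. A reader might infer that candidate factors will be screened without regard to age and sex, and that real comorbidity risk factors will be lost before any adjusted model is fitted. The documents do not support that, for these reasons:

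- Univariate screening is one of two routes and neither is chosen. Stepwise selection works within a multivariable model.
- Matching factors are examples, and the final list is left to the SAP. A one-covariate conditional model within age- and sex-matched sets would already control both. The wish for demographic odds ratios does not rule such matching out, because Table 1 also counts race/ethnicity, region and payer as demographics.
- The selection rule most naturally applies only to the empirically identified group. The Section 9.3 comorbidities may enter without passing a screen.
- The age-group repeats would recover the factor in the base scenario, which has no confounding within its two strata. Power is about 48% under 40 and 79% from 40, so the chance that at least one is significant is 1 − 0.52×0.21 = 89%.
- A uniformly young case mix is not given. For post-infection myocarditis, Section 7 quotes the highest risk in males of 30 or older, so Cohort 2 need not show this pattern.

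All of this stands against the stronger reading. It does not remove the narrower point. The univariate route is named for the primary analysis and carries no condition. The Section 9.3 sentence is permissive and so protects no factor. The subgroup repeats are secondary, use broad bands not yet fixed, and repeat the same screen, so the screen within each sex would still be unadjusted for age. The point concerns an unsafe method that the protocol authorises; leaving the matching list to the SAP is no fault in itself.

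**Conclusion.** The point holds in conditional form. The protocol authorises selection by univariate significance without requiring control of age and sex, both of which it names as established risk factors in a study of all ages. If that route is used with age and sex unmatched, age-related comorbidities can be masked and null ones can look protective.

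In the base scenario a true odds ratio of 2.0 appears as 0.96, with 6% against 92% power, and a null factor appears as 0.53. In the alternative scenarios with 3% and 20% prevalence and 55% to 80% of cases under 40, the crude value runs from 0.84 to 1.46. These sizes rest wholly on assumed age mixes, prevalences and control ratio. They say nothing quantitative about sex. Masking is small when age is matched or the comorbidity is not age-related. The planned subgroup repeats and the optional entry of Section 9.3 factors are partial safeguards.

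**What to change.** In Section 9.7 and the abstract, do one of the following:

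1. Delete the univariate-significance route.
2. State that every screening model and every stepwise step keeps age (in a flexible form) and sex as terms that cannot be removed. The exception is when both are matching factors; their main-effect odds ratios are then not reported.

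Whether to match on age and sex, and whether to add an age-by-sex interaction, can stay with the SAP. The change needs wording only and no new data. Its statistical cost is a few degrees of freedom per screening model.
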